6.4 Treatments administered

Subjects screened and eligible for the Active Phase of the study will have diagnosis of the affected disc to normal standard procedures for all treatment groups. At the baseline visit (Day 0) of the Active Phase, eligible subjects who are randomized into allograft or placebo treatment will undergo a transplantation procedure. This procedure will consist of the following:

- 1. Transplant supplemental viable allograft into the affected disc
- 2. Transplant placebo saline treatment as alternative arm of study.

These procedures are outlined in detail in Appendices B and C respectively.

At 24-months, placebo saline subjects and active allograft subjects are eligible to receive the allograft injection.

6.5 Identity of investigational product(s)

The product is generated from human allograft nucleus pulposus containing viable cells. Each product is individually prepared but is not specific for the patient being treated. The details for the preparation of cells and supplemental allograft are described in Appendix C.

6.6 Selection of the study dose

A minimum of 6*10⁶ cells will be suspended in 2 ml of matrix (NP). The investigator will ensure delivery of the dose available to reach highest possible benefit for the subject, i.e., volume

CONFIDENTIAL	Clinical Protocol	DATE	Р	age
		9Dec2019		
	mented Disc Regeneration in the Treatment of the or without Intervertebral Disc Herniation –	WRITER TG, DB, PW	NO. 27	REV 6

available degenerative disc being patient specific, and subsequent to Pfirrmann scoring, desiccation, and volume that can be delivered.

The volume of material has been derived from previous studies that have shown volume, cell density, and deliverability to be important criteria that demonstrate clinical differences. Subjects enrolled and randomized to receive the viable allograft will receive one injection of approximately 6*10⁶ cells mixed in a 1:1:0.75 by-volume ratio of cells:saline:matrix (NP) injected into the center of the affected disc(s) in the location of the nucleus pulposus. No more than 2.0 ml will be available for injection at each level into the nucleus pulposus of the symptomatic disc, or discs.

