8.4.1 Transplant of supplemental allograft into the affected disc

All subjects randomized to active allograft will undergo an intervertebral lumbar injection into the target disc. The procedure of injecting the intervertebral disc will involve placing a 22-gauge needle into the center of the affected intervertebral disc. No contrast will be used prior to the injection of the supplemental allograft and 1mL of cells (approximately 6*10⁶ cells) mixed in a 1:1:0.75 by-volume ratio (Cells in cryoprotectant: Saline: NP) will be injected into the center of the affected disc(s) in the location of the nucleus pulposus. At least 1.5-2 milliliters of the resulting mixture will be available for injection into the nucleus pulposus of the symptomatic disc. Volume injected will be recorded.

Vital signs will be recorded prior to injection. The treatment injection should be carefully controlled. The injection procedure MUST be stopped if any of the following occur:

- The investigator cannot accurately place the needle tip in the nucleus pulposus
- The subject becomes hemo-dynamically unstable during the injection procedure.

CONFIDENTIAL	Clinical Protocol	DATE	P	age
		9Dec2019		T
TITLE: V iable A llograft S upplemented Disc Regeneration in the T reatment of		WRITER	NO.	REV
Patients with Low Back Pain wit	th or without Intervertebral Disc Herniation –	TG, DB, PW	36	6
VAST-001-017				

The following information regarding the treatment procedure must be documented:

- Procedure start and stop time
- Treatment administration stop time
- Treatment interruption information, if applicable
- Total volume of treatment injected
- Pain on implantation
- Anesthesia type(s)

The information collected above will also be collected during the placebo cross over visit.

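### Protocol 6.6 and 8.4.1 give cell dose, mixing ratio and volume figures that do not agree, and leave the dose for two-level treatment unclear

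*Protocol*

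**What the plan says.** Protocol 6.6 makes three statements about the active product.

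- On the suspension: "A minimum of 6*10⁶ cells will be suspended in 2 ml of matrix (NP").
- On what each allograft subject receives: "one injection of approximately 6*10⁶ cells mixed in a 1:1:0.75 by-volume ratio of cells:saline:matrix (NP").
- On volume: "No more than 2.0 ml will be available for injection at each level".

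The same section lets the delivered volume depend on the individual disc.

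Protocol 8.4.1, which describes the procedure, adds the volume of the cell component: "1mL of cells (approximately 6*10⁶ cells) mixed in a 1:1:0.75 by-volume ratio (Cells in cryoprotectant: Saline: NP"). It then says: "At least 1.5-2 milliliters of the resulting mixture will be available for injection into the nucleus pulposus of the symptomatic disc". It requires the injected volume to be recorded and lists the total volume among the procedure data.

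Eligibility (Protocol 8.1) allows one or two levels. Protocol 6.5 refers to Appendix C for preparation details, but only the heading of that appendix is in the supplied text. SAP sections 7 to 11 plan no summary of injected volume or of cells delivered. SAP 11.3 does plan a subgroup analysis by one versus two treated levels.

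**The concern.** The cell dose defines the intervention under test, and 6.6 itself names volume and cell density among the criteria that matter clinically. If the component volumes in 8.4.1 are simply added, the mixture that holds about 6 million cells is larger than the volume that 6.6 makes available for one level. A report stating that each subject received about 6 million cells could then overstate exposure.

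Two further points bear on the same figures. The NP volume in the first sentence of 6.6 does not fit the mixing ratio. And neither section says whether 6 million is a dose per level or per subject when two discs are treated, although one versus two levels is a planned subgroup.

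The wording also matters for later treatment. Protocol 6.4 and 7.1.7 offer a further allograft injection at 24 months, and these two sections hold the only dose description in the supplied text.

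**Working it through.** **Inputs.** About 6 million cells in 1 mL of cell component (8.4.1); ratio of cells to saline to NP 1:1:0.75 by volume (6.6 and 8.4.1); ceiling of 2.0 mL per level (6.6); lower available volume of 1.5 mL (8.4.1); 2 mL of NP (6.6).

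**Assumptions.** The mix is uniform and the cell component holds about 6 million cells per mL. Whether the NP adds its full volume is not stated, so it is varied below.

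**Nominal mixture.** 1 + 1 + 0.75 = 2.75 mL. This exceeds the 2.0 mL ceiling by 0.75 mL (2.75/2.0 = 1.375, so 37.5% over).

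**Cells delivered, volumes fully additive.** Cells = 6 million × injected volume / 2.75.

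- 2.0 mL: 6 × 2.0/2.75 = 4.36 million, 27% below 6 million.
- 1.5 mL: 6 × 1.5/2.75 = 3.27 million, 45% below 6 million.

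**Sensitivity to NP volume.** Let f be the share of its 0.75 mL that the NP adds. The total is 2 + 0.75f, and a 2.0 mL injection carries 6 × 2.0/(2 + 0.75f) million cells.

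| f | Total (mL) | Cells in 2.0 mL (million) |
|---|---|---|
| 1 | 2.75 | 4.36 |
| 0.75 | 2.56 | 4.68 |
| 0.5 | 2.38 | 5.05 |
| 0.25 | 2.19 | 5.49 |
| 0 | 2.00 | 6.00 |

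The stated 6 million fits within 2.0 mL only at f = 0. At 1.5 mL even f = 0 gives 6 × 1.5/2.0 = 4.5 million.

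**Concentration that would close the gap.** With additive volumes, 2.0 mL contains 2.0/2.75 = 0.727 mL of cell component. To hold 6 million cells that component would need 6/0.727 = 8.25 million per mL, against about 6 million per mL in 8.4.1.

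**NP volume.** The ratio gives 0.75 mL of NP per 1 mL of cells, and 0.75 × 2.0/2.75 = 0.545 mL of NP in a 2.0 mL injection. Section 6.6 states 2 mL. Taking 2 mL of NP literally at the same ratio requires 2/0.75 = 2.67 mL each of cells and saline, 7.33 mL in all.

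**Two levels.** 2.0 mL at each of two levels is 4.0 mL, and one nominal mix is 2.75 mL. An even split of one preparation of 6 million cells gives at most 3 million per level.

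**The case against.** A reader might infer that 6 million cells cannot be delivered within 2.0 mL. The documents do not go that far. The second paragraph of 6.6 is consistent on its own: 0.727 mL of cells at 8.25 million per mL would satisfy it. The shortfall appears only when the 1 mL figure from 8.4.1 is added and the NP is taken to add volume. The Protocol synopsis describes the NP as micronized, and the two liquids alone make exactly 2.0 mL, so less than full additivity is possible. A preparation richer than the stated minimum would also narrow the gap. This objection stands: 27% is the fully additive end of a range at 2.0 mL, not a demonstrated loss.

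A reader might also infer that a stated minimum delivered dose is breached. The minimum in 6.6 concerns cells suspended; the sentence on what subjects receive says approximately. The proper comparison is therefore with the stated 6 million. The word approximately still does not readily cover 27%.

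Nor are the volume limits in strict contradiction. A ceiling of 2.0 mL and a floor of 1.5 to 2 mL are both met between 1.5 and 2.0 mL.

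Finally, it might be inferred that sites would give different doses, or that exposure cannot be known. The Protocol points to Appendix C, processing under a standard operating procedure (8.3), hands-on training in mixing and delivery (15.5) and a sponsor representative at each site's first two implantations (17.2), and injected volume is recorded. Divergent practice is therefore not shown. None of these sources, however, makes the printed figures in 6.6 and 8.4.1 agree.

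**Conclusion.** The dose description is wrong as written and needs correcting. Assuming a uniform mix at about 6 million cells per mL of cell component, a 2.0 mL injection carries between 4.36 million cells (NP fully additive) and 6.0 million (NP adds no volume); with additive volumes, 1.5 mL carries 3.27 million. The documents do not say where in the range at 2.0 mL the product lies.

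The mismatch between 2 mL and 0.75 mL of NP needs no mixing assumption. The volume limits overlap but are worded in opposite directions, as a ceiling in one section and a floor in the other. The dose for two levels is undefined: one nominal 2.75 mL mix cannot supply 2.0 mL to each.

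This is a defect in how the intervention is specified and how exposure would be reported. The sample size calculation does not use cell dose, and the SAP compares groups as randomised, so neither the power statement nor the planned group comparisons change.

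**What to change.** The sponsor should reconcile Protocol 6.6, 8.4.1 and Appendix C so that cell count, component volumes, total mixed volume and injectable volume per level agree arithmetically. The text should say whether the count refers to cells prepared or cells delivered, and whether it applies per level or per subject when two discs are treated. The volume limits should be expressed the same way in both sections. Which figures stand is for the sponsor to decide; none is proposed here.

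In the report, summarise the recorded injected volume, by level where it was recorded that way. Give delivered cells as an estimate, with the concentration and volume assumptions stated, instead of assuming the nominal 6 million. Two limits should be acknowledged: 8.4.1 asks for a total volume without saying per level, and the supplied text describes no cell count for each preparation. A per-level estimate may therefore not be possible for every two-level subject, and an estimate built on the nominal concentration carries the same uncertainty as the table above.

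The cost is a wording change and a little extra reporting. The stated dose may become less favourable.

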6.7 Prior and concomitant therapy

Prior complaints, surgeries, diagnostics and therapies will be documented concerning the affected intervertebral disc and other related diseases and medication. All significant medical history (as determined by investigator) must be documented regardless of when it occurred. All concomitant medication taken within 30 days prior to obtaining informed consent, and taken at any time during the study during both Screening and Active Phases will be documented on the case report forms (CRFs).

6.8 Treatment compliance

A lack of compliance during the Screening Phase will result in an exclusion from the Active Phase of the study. Once treatment occurs, a subject can only be excluded from the study due to the following:

- 1. Withdrawal of consent
- 2. Lost- to follow-up
- 3. Death
- 4. Subject undergoes subsequent surgery on the treated disc
- 5. Investigator withdrawal due to subject's study compliance

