6.3 Blinding

The assignment to treatment (active allograft, or placebo, or conservative care) is open label at Day 0 of the Active Phase to the extent that subjects receiving allograft or placebo will not be aware of what they have received, while those assigned to conservative care will be aware. All site study staff will be aware of the group to which each subject is randomized. Sites will be trained to ensure that subjects receiving the allograft or placebo treatment will remain blinded to their treatment throughout the study duration. Subjects will be unblinded during the study exit or upon signing of the new informed consent for the study extension.

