6.9 Study Duration

The study duration for all enrolled subjects in this trial is approximately 12.5 months, including a 2-week Screening Phase for enrollment following initiation of consent documentation, 12 months of follow-up after treatment in the Active Phase, and an optional long term follow up period of an additional 24 months. Study enrollment is anticipated to require approximately 3-6 months. Therefore, the total study duration will be approximately 39.5 – 42.5 months. Subjects who have unremitting pain, or worsening conditions and who had been randomized to

CONFIDENTIAL	Clinical Protocol	DATE	P	age
		9Dec2019		1
TITLE: V iable A llograft S upplemented Disc Regeneration in the T reatment of		WRITER	NO.	REV
Patients with Low Back Pain wit	th or without Intervertebral Disc Herniation –	TG, DB, PW	28	6
VAST-001-017				

the conservative group will be evaluated clinically and be given the option to crossover into the allograft supplement group. All randomized subjects will have the option to receive the allograft treatment during the optional long term follow up at 24 months. These subjects will fill out questionnaires at 36 months and have the opportunity to do so over the phone.

This study may be terminated by the sponsor if deemed necessary and documented by an amendment to this protocol. If the study is terminated, the sponsor will support follow-up of those subjects who entered the study as though the study had not been terminated.

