6.10 Subject Withdrawal and Replacement

Subjects may withdraw from the study at any time without penalty and for any reason without prejudice to their future medical care. In all cases, the reason(s) for withdrawal, and the primary reason, must be recorded on the appropriate case report form (CRF). If a subject is prematurely withdrawn from the study after randomization (Day 0 of the Active Phase), the investigator must document the reason(s) and make every effort to perform a final Termination Visit. The procedures to be followed for the Termination Visit are the same as those defined for the Month 12 Visit.

Subjects that are consented, screened and randomized, but do not undergo a successful transplantation (Day 0 of the Active Phase) will be considered screen failures. These randomization assignments will be re-used. The randomization and the replacement of subjects will be orchestrated through a 3rd party designated independent of the data collection or analysis.

CONFIDENTIAL	Clinical Protocol	DATE	Р	age
		9Dec2019		
Patients with Low Back Pain with	mented Disc Regeneration in the $\underline{\mathbf{T}}$ reatment of th or without Intervertebral Disc Herniation –	WRITER TG, DB, PW	NO. 29	REV 6
VAST-001-017				

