8.4 Study Procedure

On Day 0 of the Active Phase, eligible subjects will undergo transplantation of supplemental allograft, or saline (placebo), or continue active standard of conservative care. This conservative care procedure will not be defined by this protocol however standard practice is to be followed by each physician. All subjects who undergo successful treatment will continue in the study and be followed as per the standard of care. Subjects randomized to continuing conservative care will be assessed at 3 months, and clinical indices will be assessed. These conservative care subjects who have experienced a significant decline in condition defined as a 10% increase in pain by VASPI, or a 9-point increase in ODI will be offered the allograft as a crossover. If the subject does not meet the aforementioned changes in ODI or VASPI, or is considering withdrawal, they may be offered the allograft treatment by physician discretion if condition has significantly declined.

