7.3 METHODS FOR WITHDRAWALS AND MISSING DATA

The primary endpoint analyses will be analyzed using all available data in the mITT population. An additional sensitivity analysis will be performed for the primary endpoints using last observation carried forward (LOCF) in the mITT population.

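### Protocol 6.8 lets an investigator who knows the arm end a treated subject's follow-up for poor compliance, with no criteria, so Month 12 outcomes can be lost selectively

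*Protocol*

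**What the plan says.** Protocol 6.8 opens its list with "Once treatment occurs, a subject can only be excluded from the study due to the following". Reasons 1 to 3 are withdrawn consent, loss to follow-up and death. Reason 4 is later surgery on the treated disc. Reason 5 is "Investigator withdrawal due to subject's study compliance", with no threshold, no number of missed visits and no independent review.

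Protocol 6.3 on who knows the arm: "All site study staff will be aware of the group to which each subject is randomized". Injected subjects are blinded; conservative-care subjects are not.

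On exposure, Protocol 6.6 says allograft subjects "will receive one injection of approximately" the stated cell number, and 6.4 places the saline injection at the same Day 0 visit. For the third arm, Protocol 8.4 says "This conservative care procedure will not be defined by this protocol".

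On withdrawal after randomization, Protocol 6.10 has the investigator document the reason and "make every effort to perform a final Termination Visit", using the Month 12 procedures.

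The co-primary endpoints are the changes in ODI and VASPI at 12 months (SAP 3.2.1, 9.1). On missing values SAP 7.3 says: "The primary endpoint analyses will be analyzed using all available data in the mITT population". LOCF in the same population is a sensitivity analysis.

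**The concern.** An injected subject has no further study treatment to comply with, only visits and questionnaires. Excluding that subject for poor compliance therefore stops no treatment and mainly ends scheduled outcome collection. The decision is discretionary and the person making it knows the arm. If subjects doing badly on allograft were removed more readily than others, the Month 12 comparison would favour allograft on both co-primary endpoints, and the primary analysis would contain nothing to correct it. The loss would be avoidable, because the visits are already scheduled and the SAP already has a per-protocol set for examining non-adherence.

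**Working it through.** **Tracing one excluded subject through the plan**

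- The subject is injected on Day 0 and excluded under reason 5 before Month 12.
- A Termination Visit is attempted. Section 6.10 does not fix its date, and the SAP does not say whether its scores can stand as Month 12 values. The likely result is no Month 12 value, so the subject contributes nothing to the primary test.
- LOCF can use an earlier score if there is one. Appendix A gives the Month 1 visit to the first 24 subjects only, so other injected subjects have no scheduled post-treatment score before Month 6. If excluded earlier without a Termination Visit, they fail the mITT condition of one valid post-treatment assessment (SAP 6.2), and LOCF in the mITT set cannot recover them.

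**Planning inputs** (Protocol 13.3, SAP 4): SD 15.5, relevant difference 9 ODI points, arms of 140, 40 and 40. The plan's probability reproduces: Φ(−9 / (15.5 × √2)) = 0.341.

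**Is the lost number of subjects the main problem?** Pairwise Wilcoxon power by Noether's formula is Φ(|p − 0.5| × √(12 n₁n₂/(n₁+n₂)) − 1.96). At 140:40 this is Φ(0.159 × 19.32 − 1.96) = 87%. With random loss of 10%, 15% and 20% in both arms it is 83%, 81% and 78%. Random loss up to about 15% leaves power near 80%, so the issue is bias. (At 40:40 the same formula gives 69%, not the stated 80%; that is a separate matter and does not enter here.)

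**Size of the bias.** Assume a fraction f of the allograft arm is removed, drawn at random from the worst share w of its outcomes, with normal changes, SD 15.5, no true effect and no removal in the other arms. The removed subjects lie on average 15.5 × φ(z_w)/w below the arm mean, so the remaining mean rises by f/(1 − f) times that.

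- w = 0.25: 15.5 × 0.3178/0.25 = 19.70. For f = 5%, × 0.0526 = 1.04. For f = 10%, × 0.1111 = 2.19.
- w = 0.50: 15.5 × 0.3989/0.50 = 12.37. For f = 5%, × 0.0526 = 0.65. For f = 10%, × 0.1111 = 1.37.

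A simulation of the same setting (6,000 runs, three-arm Kruskal-Wallis at 0.05 on the remaining data) gives:

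| Removed from allograft | Drawn from | Bias, ODI points | False-positive rate |
|---|---|---|---|
| none | – | 0.0 | 4.6–5.0% |
| 5% (7 of 140) | worst half | 0.65 | 5.3% |
| 10% (14 of 140) | worst half | 1.35 | 8.1% |
| 5% | worst quarter | 1.05 | 7.2% |
| 10% | worst quarter | 2.18 | 14.0% |

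These rates are for one endpoint. Success requires both ODI and VASPI to be significant (SAP 9.1), so the joint rate is no higher.

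**The case against.** Several safeguards exist. Protocol 14.4 follows every adverse event until it resolves, reaches a new baseline, is explained or the patient is lost. The Termination Visit seeks ODI and VASPI. SAP 7.2 tabulates withdrawals by reason and SAP 7 reports by treatment group, so uneven use of reason 5 could be seen. LOCF may pick up Termination Visit scores. All of this stands and limits undetected bias, but none of it supplies a Month 12 value.

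Frequency and direction are also unknown. The documents give no withdrawal rate, and a subject who has recovered may skip visits as readily as one doing badly. At the mild end of the range, 5% removed from the worst half, there is no visible inflation of the false-positive rate. Where poor compliance means missed visits, continued contact may recover only part of the data.

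Stronger readings are tempting but not supported:

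- A reader might infer that 6.8 contradicts 6.9, where the sponsor undertakes to support "follow-up of those subjects who entered the study as though the study had not been terminated". That passage concerns termination of the whole study, whereas 6.8 concerns one subject. Both can hold.
- A reader might infer that the Termination Visit is the only data sought after exclusion. Protocol 14.4 shows otherwise for adverse events.
- A reader might take removal of exactly the worst 3%, 5% or 10% as the size. The mean then shifts by 15.5 × φ(z_f)/(1 − f) = 1.1, 1.7 or 3.0 points. That is an extreme case on a scale the rank test does not use; the median shifts by 15.5 × Φ⁻¹((1 + f)/2) = 0.58, 0.97 or 1.95.
- The argument that treatment is complete fits the two injection arms only; conservative care is ongoing.

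**Conclusion.** The point holds as a design weakness. The plan permits an investigator who knows the arm to end a treated subject's follow-up on an undefined compliance judgement, and the primary analysis then proceeds without that subject's Month 12 outcome. Nothing in the documents shows that this has happened or would favour one arm. If 5–10% of allograft subjects were removed from the worst half or worst quarter of outcomes, the bias would be about 0.7–2.2 ODI points against a relevant difference of 9, with a single-endpoint false-positive rate of about 5–14%. The removal rates, the one-sided pattern of removal, normality and the use of 15.5 as the SD of the change are assumptions. The change is worth making because it is cheap and removes an avoidable source of bias.

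**What to change.** 1. In Protocol 6.8, delete reason 5 as a ground for ending follow-up. Record poor compliance as a protocol violation and review it for the per-protocol set (SAP 6.3, 7.4). SAP 7.4 does not define a major violation, so add a sentence saying when non-compliance counts as one.
2. Keep seeking ODI, VASPI, adverse events, hospitalisation and re-operation at the scheduled Month 6 and 12 visits unless the subject withdraws consent, dies or is lost to follow-up.
3. Apply the same continued data collection to subjects excluded under reason 4. Re-operation at 12 months is a stated endpoint (SAP 3.2.2), and ending follow-up at surgery on the treated disc works against it.
4. State in SAP 7.3 how Termination Visit scores are used: whether any can count as Month 12 values, and whether the rest enter LOCF.
5. The SAP was approved in January 2020, so some subjects may already have been withdrawn. For these, report compliance withdrawals by arm.

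The cost is a few lines of protocol and SAP text, some contact effort at visits already scheduled, and some late or partial questionnaires. No treatment changes.
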